Appendix 2. Clinical Laboratory Tests

Coagulation – local laboratory

Activated partial thromboplastin time (aPTT) or partial thromboplastin time (PTT)

International normalized ratio (INR) or prothrombin time (PT)

Clinical chemistry – local and central laboratory

Serum concentrations of:

- Alanine aminotransferase (ALT)
- Albumin
- Alpha-fetoprotein (AFP; required only for patients with HCC)
- Alkaline phosphatase
- Aspartate aminotransferase (AST)
- Amylase^b
- Bicarbonate
- Bilirubin, direct
- Bilirubin, total
- Blood urea nitrogen (BUN) or blood urea
- C-reactive protein
- Calcium
- Chloride
- Creatinine
- Creatine kinase (CK)^b
- Gamma glutamyl transferase (GGT)^b
- Glucose, random
- Lactate dehydrogenase (LDH)^b
- Lipase^aLipase^b
- Magnesium
- Phosphorus
- Potassium
- Sodium
- Total protein
- TSH or free T4

Appendix 4. Sampling Schedule

It is essential that the exact infusion start and stop times (actual clock readings), as well as infusion parameters (such as, type of infusion pump, flow rate settings) are recorded. The exact time of collection of each venous blood sample will be based on the clock used to record infusion times. Preferred time windows for each sample collection are provided in the tables in this appendix.

...

Phase 1a and 1b: Pharmacokinetic, Pharmacodynamic, Immunogenicity, Biomarker, Pharmacogenomic, and ECG Collection Time Points (All Cohorts)

Cycle/Day	Study Day	Sample Time (Relative to START of LY3415244 Infusion)	PK ^{a, b}	PD sTIM-3/ sPD-L1 ^{a, b}	IG ^a	Whole Blood (PGx)	Biomarker Collection				ECG
							Plasma	Whole Blood ^c	Serum	Tissue	
...
C1D2	2	24 hours post START of LY3415244 infusion 
 • PK/PD and biomarkers: collect sample. • ECGs: perform triplicate ECG immediately before the PK sample 	X	X				X	X		X ^d
C1D4	4	72 hours post START of LY3415244 infusion 
 • PK/PD: collect sample. 	X	X							
C1D6	6	120 hours post START of LY3415244 infusion 
 • PK/PD: collect sample. 	X	X							
C1D8	8	168 hours post START of LY3415244 infusion 
 • PK/PD and biomarkers: collect sample. 	X	X			X	X	X		
C1D15	15	0 hour predose 
 • PK, PD, IG, and biomarkers: collect samples ≤2 hours prior to start of LY3415244 infusion • ECGs: Perform triplicate ECGs: 
 ○ Immediately prior to the start of the LY3415244 infusion. ○ After LY3415244 infusion is completed but before the blood draw for the PK sample 	X	X	X			X	X		X ^d

Phase 1a and 1b: Pharmacokinetic Pharmacodynamic Immunogenicity Biomarker Pharmacogenomic and ECG Collection Time Points (All Cohorts)

Cycle/Day	Study Day	Sample Time (Relative to START of LY3415244 Infusion)	PK ^{a, b}	PD sTIM-3/ sPD-L1 ^{a, b}	IG ^a	Whole Blood (PGx)	Biomarker Collection				ECG
							Plasma	Whole Blood ^c	Serum	Tissue	
C1D15	15	2 hours post start of LY3415244 infusion • PK/PD: collect sample after LY3415244 infusion is completed. • ECGs: Perform triplicate ECGs: Immediately prior to the start of the LY3415244 infusion . • After LY3415244 infusion is completed but before the blood draw for the PK sample	X	X							X ^d
...							
C1D16	16	24 hours post start of LY3415244 infusion • PK/PD: collect sample .	X	X							
C1D18	18	72 hours post start of LY3415244 infusion • PK/PD: collect sample . • ECGs: perform triplicate ECG immediately before the PK sample	X	X							X ^d
C1D20	20	120 hours post start of LY3415244 infusion • PK/PD: collect sample .	X	X							
C1D22	22	168 hours post start of LY3415244 infusion • PK/PD and biomarkers: collect sample .	X	X				X	X		

Phase 1a and 1b: Pharmacokinetic Pharmacodynamic Immunogenicity Biomarker Pharmacogenomic and ECG Collection Time Points (All Cohorts)

Cycle/Day	Study Day	Sample Time (Relative to START of LY3415244 Infusion)	PK ^{a, b}	PD sTIM-3/ sPD-L1 ^{a, b}	IG ^a	Whole Blood (PGx)	Biomarker Collection				ECG
							Plasma	Whole Blood ^c	Serum	Tissue	
...
C4D1; then Q3 cycles	85, 106 , 169 , 127 , 253 , etc.	0 hour predose • IG: collect samples \leq 2 hours prior to start of LY3415244 infusion			X						
...
30 days post last LY341524 4 dose		Anytime • PK/PD and Biomarkers: collect at any time	X	X	X		X				X ^d

Abbreviations: ADA = antidrug antibody; C = Cycle; D = Day; DLT = dose-limiting toxicity; ECG = electrocardiogram; IG = immunogenicity; IRR = infusion-related reaction; PD = pharmacodynamics; PGx = pharmacogenomics; PK = pharmacokinetics; Q = every; sPD-L1 = soluble programmed death ligand 1; sTIM-3 = soluble T-cell immunoglobulin and mucin-domain-containing molecule-3; W = week.

^a ...

^b The 2-, 4-, 24-, 72-, 120-, and 168-hour samples are **relative to the START** of the corresponding dosing event. These samples must be collected after completion of the infusion. Allowable sampling windows for 2-, 4-, 24-, 72-, 120-, and 168-hour are \pm 30 minutes, \pm 60 minutes, \pm 8 hours, \pm 24 hours, \pm 24 hours, and \pm 48 hours, respectively. Samples at 30, 60, and 90 days post last LY3415244 dose have allowable sampling windows of \pm 7 days. However, it is essential that the exact infusion start and stop times (actual clock readings), as well as infusion parameters (such as, type of infusion pump, flow rate settings) are recorded.

^c ...

^d Triplicate ECGs should be conducted after the patient has been supine for 5 minutes; collect at a minimum of 1-minute intervals, with all 3 replicate ECGs completed within 5 to 15 minutes.

Appendix 8. Definition of Woman of Childbearing Potential

Definitions:

Woman of Childbearing Potential (WOCBP)

A female is not considered to be of childbearing potential due to surgical sterilization confirmed by medical history (at least 6 weeks post-surgical bilateral oophorectomy with or without hysterectomy or tubal ligation) or menopause.

Menopausal women include women with either:

- a. spontaneous amenorrhea for at least 12 months, not induced by a medical condition such as anorexia nervosa, and not taking medications during the amenorrhea that induced the amenorrhea (for example, oral contraceptives, hormones, gonadotropin-releasing hormone, antiestrogens, selective estrogen receptor modulators, or chemotherapy), or
- b. spontaneous amenorrhea for 6 to 12 months and a follicle-stimulating hormone level >40 mIU/mL.

For individuals with permanent infertility due to an alternate medical cause other than the above, (for example, mullerian agenesis, androgen insensitivity), investigator discretion should be applied to determining study entry.

Note: Documentation can come from the site personnel's review of the participant's medical records, medical examination, or medical history interview.

Exceptions to those listed above would be if female and of childbearing potential, has a negative serum or urine pregnancy test within 7 days prior to the first dose of study medication, agrees to use a highly effective method of birth control during the study and for 6 months following the last dose of the study drugs, and is not breastfeeding. If the urine pregnancy test is positive or cannot be confirmed as negative, a serum pregnancy test will be required.

Appendix 10. Protocol Amendment J1C-MC-JZDA(b) Summary

Overview

Protocol J1C-MC-JZDA, A Phase 1a/1b Study of LY3415244, a Bispecific Antibody in Patients with Advanced Solid Tumors has been amended. The new protocol is indicated by Amendment (b) and will be used to conduct the study in place of any preceding version of the protocol.

The overall changes and rationale for the changes made to this protocol are as follows:

- Section 1. – Added clarification in the Rationale section
- Section 2. – Removed redundant vital signs from the “Physical examination” instructions in Table JZDA.2.1
- Section 5.2. – Clarified that during the Phase 1a DLT assessment period, a maximum of 10 patients per dose, may be enrolled
- CCI
- Section 6.1. – Clarified language in criterion [4]; deleted thyroid restriction in criterion [9] in order to allow patients with manageable thyroid stimulating hormone in the study; and clarified language in criterion [13] regarding effective contraceptive methods of birth control, per Belgium competent authority request
- Section 6.4. – Clarified instructions for repeat laboratory tests during screening
- Section 7.4. – Updated dose modification guidelines and AE management in Table JZDA.7.4 for Endocrine and Hepatobiliary SOCs
- Section 9.8.1. – Added text to clarify that biopsies should not be taken from areas that have been previously irradiated, unless the previously irradiated area has progressed
- Appendix 1. – Added text for clarification for highly effective methods of contraception
- Appendix 4. – Clarified sampling schedule for IG at “C2D15; then, Q2W”; “C3D1”; and “30 days post last LY3415244 dose” and clarified sampling windows for PK and pharmacodynamics sample collection in footnote “b” and timing of ECGs in footnote “d”
- Minor editorial changes were incorporated that may not be included in this summary

Revised Protocol Sections

Note: Deletions have been identified by ~~strike-throughs~~.
Additions have been identified by the use of double underscore.

Section 1. Synopsis

Rationale:

T-cell immunoglobulin and mucin-domain-containing molecule-3 (TIM-3), a co-inhibitory molecule, is expressed on T cells during activation and has been identified as a cell surface marker for “exhausted” T cells following chronic exposure to antigen (Wherry 2011) and marks the most exhausted or dysfunctional populations of T cells in the tumor microenvironment and during chronic viral infection. TIM-3 is often co-expressed with PD-1 and cytotoxic T-lymphocyte antigen 4 on tumor-antigen-specific T cells in cancer patients. Blocking TIM-3 provides the opportunity to enhance antitumor T-cell immunity, much like targeting the PD-1 axis, and provides the opportunity to combine anti-TIM-3 therapy with clinically validated checkpoint inhibitor antibodies such as PD-1 or PD-L1.

Section 2. Schedule of Activities

Table JZDA.2.1. Baseline and On-Study Treatment Schedule of Activities

	Baseline (Day Relative to C1D1)		Cycle 1		Cycle 2		Cycle 3		Cycle 4-n		Instructions: Perform all cycle-related procedures on the specified day (± 3 days), unless stated otherwise in this schedule of activities. See Section 7 regarding administration of study treatment.
	≤ 28	≤ 7	D1	D15	D1	D15	D1	D15	D1	D15	
Procedure											
Informed consent	X										ICF must be signed before any protocol-specific procedures are performed
Inclusion/exclusion criteria	X										
Medical history	X										Including assessment of preexisting conditions and historical illnesses
Cancer treatment history	X								Record prior anticancer therapy		
Concomitant medication	X		X						
 At baseline, record prior and concurrent medications Record all premedication, supportive care, and concomitant medication continuously throughout the study 		
Physical examination	X		X		X		X		X		
 At baseline, perform full examination including recent medical history, height, and weight and vital signs (temperature, blood pressure, pulse rate, and respiration rate) Thereafter, perform a focused examination, including weight and vital signs For vital sign measurements, see additional instructions below

Section 5.2 Number of Patients

Enrollment in each cohort will be adjusted if needed to allow adequate assessment of safety and preliminary antitumor activity at the LY3415244 RP2D.

- **Phase 1a:** Total enrollment will be determined by the incidence of DLTs.
 - Cohorts A1 through A8: approximately 27 patients (minimum of 3 patients per cohort) will be enrolled. During Phase 1a DLT assessment period, a maximum of 10 patients per dose level, may be enrolled.

CCI

Section 6.1 Inclusion Criteria

- [4] Patients with mesothelioma are not required to have received prior anti-PD-1 or anti-PD-L1 therapy. If the patient has received prior anti-PD-1 or anti-PD-L1 therapy, then inclusion criteria [2]a through [2]d and [3]a and [3]b would apply. Additionally, patients must have:
 - a. confirmed unresectable or medically inoperable malignant ~~pleural~~ mesothelioma (~~MPM~~) subtype and progressive disease (PD) after at least one prior systemic treatment with a platinum-based doublet (both cisplatin and carboplatin are allowed) for unresectable MPM. All prior cytotoxic toxicities must have resolved to Grade ≤ 2 prior to registration.

Section 6.1 Inclusion Criteria

[9] Have adequate organ function as defined in the table below:

System	Laboratory Value
Hematologic	
ANC	$\geq 1.5 \times 10^9$ cells/L
Platelets	$\geq 100 \times 10^9$ /L
Hemoglobin	≥ 9 g/dL At the discretion of the investigator, patients may receive erythrocyte transfusions to achieve this hemoglobin level; however study treatment may not begin until 2 days after erythrocyte transfusion and after confirmation of hemoglobin ≥ 9 g/dL.
aPTT	$\leq 1.5 \times$ ULN
Hepatic	
Total bilirubin	$\leq 1.5 \times$ ULN OR $< 3.0 \times$ ULN for patients who have Gilbert's syndrome
ALT and AST	$\leq 2.5 \times$ ULN OR $\leq 5 \times$ ULN if the liver has tumor involvement
Renal	
Serum creatinine OR Calculated creatinine clearance (see Appendix 6)	$\leq 1.5 \times$ ULN OR ≥ 50 mL/min
Thyroid	
TSH or free T4	Within normal limits

Abbreviations: ALT = alanine aminotransferase; ANC = absolute neutrophil count; aPTT= activated partial thromboplastin time; AST = aspartate aminotransferase; ULN = upper limit of normal; T4= thyroxine; TSH = thyroid stimulating hormone

Section 6.1 Inclusion Criteria

[13] Men with partners of childbearing potential or women with childbearing potential must agree to use a highly effective contraceptive methods of birth control (Appendix 1) during study treatment and for at least 6 months following the last dose of study drug. (eg, intrauterine device, birth control pills, or barrier method). If condoms are used as a barrier contraceptive, a spermicidal agent should be added as double barrier protection.

Section 6.4 Screen Failures

Repeating laboratory tests (including ECGs) that did not meet eligibility criteria during the 28-day baseline screening period does not constitute rescreening. However, laboratory tests may not be repeated more than twice, and. If the results of a repeated laboratory test must meet the eligibility criteria, an additional laboratory test must be repeated again to confirm eligibility.

Section 7.4 Dose Modification

Table JZDA.7.4 Dose Modification Guidelines and AE Management for Toxicities At Least Possibly Related to Study Drug

SOC	Toxicity	CTCAE Grade and/or Symptoms ^a		Treatment Plan ^b
		Grade	Symptoms	
Endocrine	Thyroid issues		If asymptomatic with TSH $<0.5 \times$ LLN or $>2 \times$ ULN	Continue study treatment, perform free T4 in subsequent eyeles, and begin medical management as needed
			If symptomatic	
 Start thyroid replacement therapy and/or medical management and continue study treatment For Grade 3 hyperthyroidism, withhold study treatment until hyperthyroidism improves to Grade ≤ 1 For Grade 4 hyperthyroidism, discontinue study treatment

SOC	Toxicity	CTCAE Grade and/or Symptoms ^a		Treatment Plan ^b
		Grade	Symptoms	
Hepatobiliary	Transaminitis, elevated bilirubin	2	
 AST or ALT between $2.5 \times$ ULN and $5 \times$ ULN, or TB between $1.5 \times$ ULN and $3 \times$ ULN 	
 Withhold study treatment and administer prednisone 1-2 mg/kg/day Resume study treatment after symptoms resolve to Grade ≤ 1
			
 AST or ALT $>5 \times$ ULN, or TB $>3 \times$ ULN 	
 Discontinue study treatment and administer IV methylprednisolone 2-4 mg/kg/day If the event continues for >3 days despite corticosteroids, add a nonsteroidal immunosuppressive agent^c

Section 9.8.1 Tissue Samples for Biomarker Research

An attempt to obtain 4 core-needle biopsies or a surgical biopsy is required, unless medically contraindicated and discussed with Lilly CRP/CRS. Optimally, biopsies should be taken from the same lesion and from areas not previously irradiated. Biopsies should not be taken from areas that have been previously irradiated, unless the previously irradiated area has progressed.

Appendix 1 Abbreviations and Definitions

highly effective methods of contraception

Methods include:

- Combined (estrogen and progestogen containing) hormonal contraception associated with inhibition of ovulation:
 - o oral
 - o intravaginal
 - o transdermal
- Progestogen-only hormonal contraception associated with inhibition of ovulation :
 - o oral
 - o injectable
 - o implantable
- Intrauterine device (IUD)
- Intrauterine hormone-releasing system (IUS)
- Bilateral tubal occlusion
- Vasectomized partner (vasectomized partner is a highly effective birth control method provided that partner is the sole sexual partner of the woman of childbearing potential who is the trial participant and that the vasectomized partner has received medical assessment of the surgical success.)
- Sexual abstinence (sexual abstinence is considered a highly effective method only if defined as refraining from heterosexual intercourse during the entire period of risk associated with the study treatments. The reliability of sexual abstinence needs to be evaluated in relation to the duration of the clinical trial and the preferred and usual lifestyle of the subject.)

~~combined oral contraceptive pill and mini pill, NuvaRing®, implantable contraceptives, injectable contraceptives (such as Depo Provera®), intrauterine device (such as Mirena® and ParaGard®), contraceptive patch for women <90 Kg (<198 pounds), total abstinence, or vasectomy.~~

~~Also see the definition of effective method of contraception.~~

Appendix 4 Sampling Schedule

Phase 1a and 1b: Pharmacokinetic, Pharmacodynamic, Immunogenicity, Biomarker, Pharmacogenomic, and ECG Collection Time Points (All Cohorts)

Cycle/Day	Study Day	Sample Time (Relative to START of LY3415244 Infusion)	PK ^{a, b}	PD sTIM-3/ sPD-L1 ^{a, b}	IG ^a	Whole Blood (PGx)	Biomarker Collection				ECG
							Plasma	Whole Blood ^c	Serum	Tissue	
C2D15; then, Q2W	43, 57, 71, etc.	0 hour predose • PK/PD, IG : collect samples ≤2 hours prior to start of LY3415244 infusion	X	X							
C3D1	57	0 hour predose • IG Biomarkers : collect samples ≤2 hours prior to start of LY3415244 infusion. • ECGs: perform triplicate ECG at the following time points: ○ Prior to start of LY3415244 infusion ○ At the end of the LY3415244 infusion			X		X	X	X	X ^d	

Cycle/Day	Study Day	Sample Time (Relative to START of LY3415244 Infusion)	PK ^{a, b}	PD sTIM-3/ sPD-L1 ^{a, b}	IG ^a	Whole Blood (PGx)	Biomarker Collection				ECG
							Plasma	Whole Blood ^c	Serum	Tissue	
30 days post last LY341524 4 dose		Anytime • PK, PD, IG , and biomarkers: collect at any time	X	X	X		X				X ^d

- b The 2-, 4-, 24-, 72-, 120-, and 168-hour samples are **relative to the START** of the corresponding dosing event. These samples must be collected after completion of the infusion. Allowable sampling window for pre-dose C1D1 is -8 hours. Allowable sampling windows for 2-, 4-, 24-, 72-, 120-, and 168-hour are ± 30 minutes, ± 60 minutes, ± 8 hours, ± 24 hours, ± 24 hours, and ± 48 hours, respectively. If LY3415244 infusion need to be increased up to 2 hours the allowable sampling windows for the 2-hour sample is increased to +60 minutes. Samples at 30, 60, and 90 days post last LY3415244 dose have allowable sampling windows of ± 7 days. However, it is essential that the exact infusion start and stop times (actual clock readings) are recorded.
- d Triplicate ECGs should be conducted immediately before the PK sample and after the patient has been supine for 5 minutes; collect at a minimum of 1-minute intervals, with all 3 replicate ECGs completed within 5 to 15 minutes.

Leo Document ID = 4fea25e9-b30b-4192-93a9-54003b208979

Approver: PPD

Approval Date & Time: 12-Dec-2018 15:40:27 GMT

Signature meaning: Approved

Approver: PPD

Approval Date & Time: 13-Dec-2018 01:11:44 GMT

Signature meaning: Approved

4.1. Primary Objective

Phase 1a: To assess the safety and tolerability of LY3415244 in patients with advanced solid tumors, thereby identifying a recommended Phase 2 Dose (RP2D) to be administered to patients in the Phase 1b portion of the study.

Phase 1b: To assess the safety and tolerability of the RP2D dose of LY3415244 in patients with advanced solid tumors.

4.2. Secondary Objectives

Phase 1a: To assess the pharmacokinetics (PK) of LY3415244.

Phase 1b:

- to assess the PK of LY3415244 in patients in each of 4 expansion cohorts.
- to assess early antitumor activity of LY3415244 in patients in each of 4 expansion cohorts.

4.3. Tertiary/Exploratory Objectives

Phase 1a and 1b:

- to characterize tumor tissue and blood biomarkers relevant to LY3415244, including but not limited to immune cells/immune functioning, mechanism of action of study drugs, cancer-related pathways, and disease state
- to explore the association between biomarkers and clinical outcomes
- to assess the immunogenicity of LY3415244
- to assess overall survival (OS) of patients receiving LY3415244 administered as monotherapy

5. A Priori Statistical Methods

5.1. Sample Size Determination

The sample size determination is described in Protocol J1C-MC-JZDA (JZDA), Section of Sample Size Determination.

5.2. General Considerations

Statistical analysis of this study will be the responsibility of Eli Lilly and Company (Lilly) or its designee.

Sponsor standard tables, figures, and listings (TFLs) and supporting programs and software (eg, SAS®) will be utilized for all analyses where a suitable standard exists. Data derivations in this SAP are defined based upon current sponsor reporting standards at the time of writing, and may be updated at the time of analysis in order to maintain accordance with the most current sponsor standards at that time.

Unless otherwise noted, **summaries of continuous variables** will include a mean, median, standard deviation, minimum, and maximum. When appropriate, lower and upper quartiles will also be presented.

Unless otherwise noted, **summaries of categorical variables** will include the frequency and percentage (relative to the population being analyzed) of each category.

In Part 1a, unless otherwise stated, data will be summarized by dose escalation cohorts which will indicate the assigned treatment regimen and dose schedule for LY3415244.

In Part 1b, unless otherwise stated, data will be summarized by expansion cohorts.

In addition, safety data may be summarized by the same treatment regimen and dose schedule, and efficacy data may be summarized by the same indication, treatment regimen, and dose schedule by combination of the Phase 1a and 1b part.

Additional exploratory analyses of the data will be conducted as deemed appropriate.

5.2.1. Populations

The following population will be defined for this study:

Entered Population: will include all patients who sign the informed consent document.

Enrolled/Safety Population: will include all patients who received any quantity of study treatment (LY3415244), regardless of their eligibility for the study. The safety and efficacy evaluation will be performed based on the first dose of study treatment a patient actually received. This population will be used for all dosing/exposure, safety, and efficacy analyses.

Dose-Limiting Toxicity (DLT)-Evaluable Population (for Phase 1a): will include all patients from Phase 1a portion of the study who have completed DLT observation period (Cycle 1) or discontinued treatment before the end of the DLT observation period but with a documented DLT assessment. Exposure and safety summaries will be repeated for this population.

Pharmacokinetic population: will include all enrolled patients from whom a valid assay result (according to laboratory guideline) has been obtained.

Biomarker population: will include the subset of enrolled patients from whom a valid assay result has been obtained. No imputation will be performed for missing data due to the limitation of small sample size.

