7.4. Dose Modification

No dose modification is allowed during Phase 1a DLT observation period (Cycle 1).

After the Phase 1a DLT observation period (Cycle 1), doses of the study drug may be delayed or discontinued to manage specific AEs or other toxicities. Dose reductions are not permitted. All dose modifications should be documented, including the approach taken and a clear rationale for the need for modification.

The investigator must assess whether the toxicity is at least possibly due to study treatment and apply the dose-modification guidelines. Investigators are encouraged to consult Lilly for additional guidance.

If a patient requires a dose delay, study treatment should be resumed within 1 cycle, if possible and appropriate. If study treatment cannot be resumed within 1 cycle, every effort should be made to restart on the first day of the next cycle. In rare circumstances, a delay of >28 days may be permitted before permanent treatment discontinuation, as long as the patient demonstrates clinical benefit, does not have objective progression, and is recovering from the toxicity. Such circumstances must be discussed with the Lilly CRP/CRS.

Adverse events of immune-related etiology are expected because of the study drug's mechanism of action and may occur shortly after the first dose or several months after the last dose. Study treatment must be withheld if the patient experiences a drug-related toxicity or a severe or life-threatening AE. Dose reductions are not permitted.

A 4-hour observation period is required after the administration of LY3415244 in Cycles 1 to 3. During observation period, patients treated with LY3415244 should be closely monitored for signs and symptoms indicative of an infusion-related reaction by medical staff from the start of the infusion until 4 hours after the end of the infusion, in an area where emergency medical resuscitation equipment and other agents (epinephrine prednisolone equivalents, etc.) are available. LY3415244 infusion-related reactions will be defined according to the Common Terminology Criteria for Adverse Events (CTCAE), Version 4.0 definition of IRRs.

Table JZDA.7.3 presents instructions for management of infusion-related reactions associated with LY3415244.

Table JZDA.7.3. Management of Infusion-Related Reactions

Grade	Management
2	First occurrence

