7.6.1.1. DLT-Evaluable Patients in Phase 1a

A patient will be DLT evaluable if he or she experiences a DLT during the DLT observation period and has received at least 1 dose of study drug.

If a patient does not experience a DLT during the DLT observation period, he or she will be DLT evaluable if he or she receives all assigned doses of study drug(s) during the DLT observation period

Patients who receive all doses of study drug but discontinue from study treatment before the end of the DLT observation period will be considered DLT evaluable for the assessment of a dose level, provided it can be documented that the patient did or did not experience a DLT within the DLT observation period.

Patients who are not DLT evaluable may be replaced to ensure that enough patients complete the DLT observation period at each dose level, unless accrual to that cohort has stopped due to a DLT.

A patient may be deemed non-evaluable for assessment of a dose level in the event the patient experiences an AE which would meet DLT criteria, and furthermore has been determined through discussion between investigator and Lilly CRP/CRS to most likely be related to a

concomitant medication or a prior line of immune therapy (in the case of irAEs) due to previously established linkage. Adverse events from DLT non-evaluable patients will also be reviewed throughout the dose escalation process in Phase 1a.

To ensure collection of adequate PK or biomarker data, patients who complete the DLT observation period but who do not have a valid PK or biomarker assay result may be replaced, upon consultation with the investigator(s) and the Lilly CRP/CRS, unless accrual to that cohort has stopped because of a DLT. Patients who are replaced for purposes of the PK or biomarker analysis are still considered DLT evaluable.

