5.12.2. Dose-Limiting Toxicity and DLT-Equivalent Toxicities

The definition of the DLTs and the DLT-equivalent toxicities (DETs) is specified in Protocol J1C-MC-JZDA (JZDA), Section of Dose-Limiting Toxicity Determination.

Dose limiting toxicities will be summarized and listed for DLT-evaluable population.

Dose limiting toxicities-equivalent toxicities (DETs) will also be listed and summarized for safety population.

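### The SAP's DLT-evaluable population drops the protocol's all-doses condition, so an under-dosed, DLT-free patient who stops early would enter the reported DLT denominator

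*SAP*

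**What the plan says.** Protocol Section 7.6.1.1 gives two routes to DLT evaluability. A patient who has a DLT in the observation period needs only one dose. For a patient who has none, "he or she will be DLT evaluable if he or she receives all assigned doses of study drug(s) during the DLT observation period". The early-discontinuation paragraph keeps the dose condition, because it covers only "Patients who receive all doses of study drug but discontinue from study treatment before the end of the DLT observation period", and it adds that DLT status must be documentable. The section then provides that "Patients who are not DLT evaluable may be replaced". It also allows a patient with a DLT-type event to be deemed non-evaluable if the event is judged most likely due to a "concomitant medication or a prior line of immune therapy (in the case of irAEs) due to previously established linkage".

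SAP Section 5.2.1 defines the DLT-evaluable population as Phase 1a patients who completed Cycle 1 or who "discontinued treatment before the end of the DLT observation period but with a documented DLT assessment". It states no dose condition and no attribution provision.

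That population is then used for the endpoint. SAP Section 5.12.2 says "Dose limiting toxicities will be summarized and listed for DLT-evaluable population", and SAP Section 5.2 says categorical summaries "will include the frequency and percentage (relative to the population being analyzed) of each category".

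**The concern.** DLTs are a Phase 1a primary endpoint, and the SAP's population definition fixes the denominator of the reported percentage. The protocol excludes DLT-free patients with incomplete Cycle 1 dosing because they have not been tested at the full assigned exposure; it replaces them. The SAP would count them as patients who tolerated the dose.

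The discrepancy works in one direction. Anyone admitted solely because the dose condition is missing is DLT-free by construction, so the reported rate can only fall or stay at 0%. The published DLT table could then disagree with the evaluable counts on which each escalation decision was made, with nothing in the SAP to explain the difference.

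**Working it through.** The plan states no figure for this point, so there is nothing to reproduce. The check compares the two definitions and then works out the effect on a proportion.

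**Inputs**
- Cycle 1 doses: two, on Days 1 and 15 (Protocol Table JZDA.7.1).
- DLT observation period: one 28-day cycle (Protocol 5.1.1).
- Patients per dose level: minimum 3, maximum 10 in the DLT assessment period (Protocol 5.2).
- Evaluability rules: Protocol 7.6.1.1 and SAP 5.2.1.

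**The two definitions applied to each type of patient**

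| Cycle 1 course | Protocol 7.6.1.1 | SAP 5.2.1 |
|---|---|---|
| DLT after at least one dose, DLT documented | evaluable | evaluable |
| No DLT, both doses, completes Cycle 1 | evaluable | evaluable |
| No DLT, both doses, stops before Day 28, status documented | evaluable | evaluable |
| No DLT, Day 1 dose only, stops before Day 15, status documented | **not evaluable** | **evaluable** |
| No DLT, Day 15 dose missed, stays to Day 28 | **not evaluable** | **evaluable**, if this counts as completing the period |
| DLT-type event judged most likely due to other therapy | may be deemed non-evaluable | no such provision |

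The fourth row is the clear conflict. The fifth should be less common, because Protocol 7.4 bars dose modification in Cycle 1.

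**Does another section close the gap?** SAP 5.12.2 refers to the protocol for what a DLT is, not for who is evaluable. Protocol 10.2 defines no DLT-evaluable set, so SAP 5.2.1 governs. Protocol 10.3 asks for changes to its analysis methods to be described and justified in the SAP and the study report; the SAP offers no justification here. Neither amendment summary records a change to the dose condition.

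**Effect on the rate.** Let x be the number of DLTs, n the protocol-evaluable patients and k the DLT-free patients admitted only by the SAP (assumed). The protocol rate is x/n and the SAP rate is x/(n+k). For k = 1 the fall is x/n − x/(n+1) = x/[n(n+1)].

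| k | Protocol x/n | SAP x/(n+k) | Fall (points) |
|---|---|---|---|
| 0 | any | unchanged | 0 |
| 1 | 1/3 = 33.3% | 1/4 = 25.0% | 8.3 |
| 1 | 2/5 = 40.0% | 2/6 = 33.3% | 6.7 |
| 1 | 2/6 = 33.3% | 2/7 = 28.6% | 4.8 |
| 1 | 3/9 = 33.3% | 3/10 = 30.0% | 3.3 |
| 1 | 1/9 = 11.1% | 1/10 = 10.0% | 1.1 |
| 2 | 1/3 = 33.3% | 1/5 = 20.0% | 13.3 |
| 2 | 2/6 = 33.3% | 2/8 = 25.0% | 8.3 |

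For n from 3 to 9, k = 1 and an observed rate between 10% and 40%, the fall runs from 1/90 = 1.1 points to 1/12 = 8.3 points. With x = 0 the estimate stays at 0%.

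**The attribution provision.** Suppose the protocol count is x/n after one patient is deemed non-evaluable on attribution, and the SAP keeps that patient. If the event is counted as a DLT, the SAP rate is (x+1)/(n+1); if not, it is x/(n+1). From 1/3 = 33.3% these give 2/4 = 50.0% and 1/4 = 25.0%. This mismatch can therefore move the rate either way.

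**The case against.** The strongest reply is that this is loose paraphrase with little consequence. The SAP wording tracks the protocol's early-discontinuation paragraph and may have been meant as a short form of it. Protocol 10.3.1 plans only the number of patients with a DLT by cohort, and extra DLT-free patients leave that number unchanged. No confidence interval or test is specified for the Phase 1a DLT rate. Escalation uses the protocol rule and Appendix 7, and under Protocol 7.2.2.3 the RP2D rests on all the data. Exposure summaries on the same population would reveal under-dosing. Clearly attributed events are already outside the DLT definition in Protocol 7.2.2.2, which SAP 5.12.2 adopts.

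Much of this stands. The count of DLTs and the escalation decisions are not at risk, the number of affected patients is unknown, and the attribution gap is confined to events judged most likely, but not clearly, due to another cause.

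It does not remove the conflict. Whatever was intended, the SAP rule as written admits a patient the protocol excludes. The undefined term for a documented assessment adds no dose requirement even when read in the protocol's sense. The protocol phrases its rule with a plain conditional, but it offers a DLT-free patient no other route to evaluability. A planned count does not displace the SAP's general percentage convention, and an exposure table does not correct a denominator.

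One caveat cuts the other way. Protocol 7.4 also requires treatment to be withheld for drug-related toxicity and does not say whether that applies in Cycle 1, so a patient who completes the cycle without the Day 15 dose cannot be ruled out.

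**Conclusion.** The point holds. On the dose condition, SAP 5.2.1 conflicts with Protocol 7.6.1.1 for a Phase 1a primary endpoint, and any resulting bias in the reported DLT rate is downward, or nil where there are no DLTs.

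The size depends on an assumption that the documents cannot settle: how many DLT-free patients stop before Day 15 with their DLT status recorded. With none, nothing changes. With one at a dose level, the fall is 3.3 to 8.3 percentage points in the examples with observed rates of 33% to 40%, and as little as 1.1 points at lower rates. The text comparison is secure; the practical effect is conditional. This should be corrected before the DLT table is produced, but it does not threaten the conduct of escalation.

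**What to change.** Replace the definition in SAP 5.2.1 with a cross-reference to Protocol 7.6.1.1 that carries over all of its elements:

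- a DLT in Cycle 1 after at least one dose; or
- no DLT, with all assigned Cycle 1 doses received and, for those who discontinue before the end of the period, documented DLT status; and
- the provision that a patient whose DLT-type event is attributed to a concomitant medication or prior immune therapy may be deemed non-evaluable.

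Beside the DLT table, list every treated Phase 1a patient excluded as non-evaluable, with the reason and the doses received, so that a reader can reconcile the reported denominators with the counts used for escalation.

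The cost is one SAP paragraph and one listing. Nothing changes at the sites or in the escalation procedure.
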